Tertiary	% of participants who complete outcome assessments upon program completion in each arm	Participants who complete outcome assessments upon program completion will be tallied. Numerator= total # of participants randomized into each arm who complete outcome assessments upon program completion.  Denominator= total # of participants randomized into each arm.
Tertiary	Mean % of CR sessions administered as intended in each arm	% of CR sessions (out of all 24 sessions) administered as intended to participants allocated to the THCR intervention and, separately, the traditional CR intervention
Tertiary	# of eligible patients referred to CR/month	# of patients who are referred to CR and eligible for the pilot study per month
Tertiary	% of participants who report adequate acceptability of the THCR intervention	% of participants who report an average score ≥4 (agree or completely agree) for their rating of the patient-perceived THCR intervention's feasibility on the four-item Acceptability of Intervention Measure (AIM). All four items of the AIM are rated on a Likert response scale ranging from 1 to 5 with higher scores indicating greater acceptability. Each Likert response scale rating will be summed (minimum: 4, maximum: 20) and averaged (minimum: 1, maximum: 5) across all four items.
Tertiary	% of participants who report adequate appropriateness of the THCR intervention	% of participants who report an average score ≥4 (agree or completely agree) for their rating of the patient-perceived THCR intervention's feasibility on the four-item Intervention Appropriateness Measure (IAM). All four items of the FIM are rated on a Likert response scale ranging from 1 to 5 with higher scores indicating greater appropriateness. Each Likert response scale rating will be summed (minimum: 4, maximum: 20) and averaged (minimum: 1, maximum: 5) across all four items.
Exploratory	Change in total distance traveled in 6MWT	This is to measure pre-to-post program change in functional capacity (using the six-minute walk test [6MWT]) among THCR and, separately, traditional CR participants. The 6MWT is a sub-maximal exercise test used to assess aerobic capacity and endurance. The total distance (meters) traveled over a time period of six minutes is used as the outcome by which to compare changes in performance capacity.
Exploratory	Change in health-related quality of life score	This is to measure pre-to-post program change in health-related quality of life (Duke health profile questionnaire [DUKE; physical, mental, social, and general health composite scores]) among THCR and, separately, traditional CR participants. The DUKE is a 17-item self-report questionnaire for measuring generic health-related quality of life over a 1-week time period. Responses are scored to calculate physical health, mental health, and social health scores, which are then summed and divided by 3 to obtain a general health score. The general health score ranges from 0 - 100, with high scores indicating better health-related quality of life.

I will use EHR and eCC data to assess feasibility metrics relevant to recruitment, retention, outcome assessments (described below), adherence, and fidelity to both the hybrid CR and traditional CR intervention. Survey data from the FIM, AIM, and IAM will be used to assess patient-perceived intervention feasibility, acceptability, and appropriateness, respectively. Data will be extracted from these sources via Trac requests, patient notes, patient chart review, and data export. Quality of administration will be assessed using direct observations throughout the trial, wherein research personnel will observe CR sessions (including onboarding sessions) and fill out a pragmatic checklist to assess fidelity. *Feasibility Criteria*. Feasibility will be achieved if the following criteria are met: (1) ≥3 eligible ACS patients are enrolled/month (recruitment); (2) ≥70% of THCR, and separately, traditional CR participants attend ≥1 CR sessions after randomization (program initiation); (3) ≥70% of THCR, and separately, traditional CR participants complete outcome assessments at 3 month follow up; (4)

 $\geq$ 50% of CR sessions ( $\geq$ 12 of 24) are completed by those allocated to each arm (adherence); (5)  $\geq$ 80% of CR sessions ( $\geq$ 20 of 24) are administered as intended for each arm (fidelity).

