These inclusion and exclusion criteria were selected based on AACVPR/ACC/AHA guidelines and previously published protocols.

**Overview of Study Design:** Patients who meet all eligibility criteria and provide consent will be enrolled into the study and randomized (1:1) to THCR (n=20) or traditional clinic-based CR (n=20). After randomization, each group will initiate the program to which they are allocated, wherein the first intervention visit for each group will be a clinic-based CR session. Each program will include 24 CR sessions over the course of 3-months. As part of standard of care, all patients will complete a six-minute walk test [6MWT], modified Balke Treadmill test, sit-to-stand test, PHQ-9, and Duke Health Profile (DUKE) questionnaire upon program completion (3-month follow up visit).

**Sample Size and Power Estimates:** Although some have used pilot studies to estimate effect sizes for primary outcomes, I agree with leaders in our field who argue that effect size estimates from small pilot studies are too imprecise to meaningfully inform effect size assumptions of power analyses for larger, later stage

studies. Therefore, I do not provide power calculations for the effects of our intervention on adherence and behavioral health outcomes. I will, however, use estimates from these studies (e.g., standard deviations, attrition rates) to help determine an appropriate sample size for a subsequent study that is adequately powered to detect meaningful improvements in measures of adherence, functional capacity, and health-related quality of life

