Clinic-based CR Evaluation (Session 24; 60 mins): All patients enrolled in the study, irrespective of program allocation, will complete a final clinic-based CR evaluation session at the NYP-VCR Clinic. The clinic-based CR evaluation session will adhere to existing standard of care protocols and will be administered by CR clinicians who have legitimate (non-research) access to patient data and who are involved in the standard of care treatment of participants. Participants enrolled in the hybrid CR program will receive a reminder phone call and/or email and be instructed to bring all RPM devices with them to their clinic-based CR evaluation session. RPM devices will then be disinfected according to Philip's Healthcare protocols.

**Post-Intervention:** After completing the last CR session (Session 24), participants will be asked to complete post-intervention questionnaires and an exit interview. To accommodate participant preference, participants will be given the option to complete the questionnaires and exit interview in-person, at the NYP-VCR clinic immediately following the last CR session or at a separate day and time via telephone. The post-intervention sessions must be completed within 1-week after CR session 24. Exceptions to the 1-week turnaround expectation will be considered on a case-by-case basis by the study PI (i.e. the participant is sick or has a planned vacation). Completion reminder attempts initiated by the research team will be documented.

**Post-Intervention Questionnaires (20 mins):** Participants will complete valid, reliable, and pragmatic 4-item surveys on the acceptability, appropriateness, and feasibility of the intervention: (1) Acceptability of Intervention Measure (AIM), (2) Intervention Appropriateness Measure (IAM), (3) and the Feasibility of Intervention Measure (FIM). They will also complete the same series of baseline questionnaires, implementation determinants questions, satisfaction questions and questions about their experience (e.g., bored, sleepy) while doing the CR sessions. The same battery of questionnaires will be administered half way into the intervention (CR Visit 12) to obtain a mid-intervention assessment.

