**Exit Interview (30-45 mins):** After each participant completes the post-intervention questionnaires, they will participate in a 30-minute exit interview. The exit interview will take place in-person or via telephone. The goal is to assess participant-level barriers and facilitators to participating in and implementing the pilot study, as well as elicit feedback on the hybrid CR intervention design. The interview will be digitally audiotaped using Zoom and transcribed using Microsoft Stream.

After all intervention sessions are complete, participants enrolled in the hybrid CR program will have the option to keep their home-based exercise equipment. If the participant forgot to bring all RPM to their last CR session (Session 24), they will receive a pre-paid package to mail back the RPM devices, which will then be disinfected according to Philip's Healthcare protocols.

Feasibility Measures (Aim 1). To determine feasibility, I will examine the endpoints outlined in Table 1.

**Table 1.** Aim 1 Outcome Measures

Measure	Measure	Measure Description
Type		
Primary	# of participants enrolled/month	# of participants who completed recruitment activities and successfully
		consented and enrolled into the pilot study per month

Primary	Mean % of CR sessions completed by THCR participants	% of CR sessions completed by participants allocated to the THCR intervention, which includes 19 home-based and 5 clinic-based sessions.
Secondary	% of participants who attend ≥1 CR session after randomization in each arm	Participants who attend ≥1 CR session will be tallied. Numerator= total # of participants randomized into each arm who attend ≥1 CR session.  Denominator= total # of participants randomized into each arm.
Secondary	Mean % of CR sessions completed by traditional CR participants	% of CR sessions completed by participants allocated to the traditional CR intervention, which includes 24 clinic-based sessions.
Secondary	% of participants who report adequate feasibility of the THCR intervention	% of participants who report an average score ≥4 (agree or completely agree) for their rating of the patient-perceived THCR intervention's feasibility on the four-item Feasibility of Intervention Measure (FIM). All four items of the FIM are rated on a Likert response scale ranging from 1 to 5 with higher scores indicating greater feasibility. Each Likert response scale rating will be summed (minimum: 4, maximum: 20) and averaged (minimum: 1, maximum: 5) across all four items.

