Aim 2 Analysis. Data from interviews will be transcribed using Microsoft Stream and I will employ thematic analysis and code for themes using a 6-phase process and NVIVO software, and adhering to the qualitative COREQ research checklists. Transcripts will be coded for barriers and facilitators to hybrid CR using the Consolidated Framework for Implementation Research (CFIR; 39 constructs within five domains [e.g., inner setting, outer setting]) and Theoretical Domains Framework (TDF; 84 theoretical constructs within 14 domains [e.g., knowledge, skills, social/professional role]). While there is considerable overlap in these theoretical frameworks, I will leverage the ways in which CFIR addresses system-level determinants and TDF addresses individual-level determinants. Two raters will review the audio and visual data for each participant. Content analysis will be used to identify patterns in the stakeholder's responses to questions about acceptability, barriers, and facilitators to THCR. I will further assess whether CR barriers and acceptability differed among those with high vs. low fidelity to THCR and among those in the THCR vs. traditional arms of the study.

**Compensation:** Participants will receive a PayCard in-person or in the mail after successfully completing the first two clinic-based CR session (CR Session 1 & 2). Once they confirm receiving the PayCard with study personnel, \$50 will be uploaded to the card as compensation for the initial clinic-based visits (payment #1). Following successful completion of CR session 12 and mid-intervention assessments, they will be compensated an additional \$50 on the PayCard (payment #2). Following successful completion of CR session 24 and post-intervention assessments, they will be compensated an additional \$50 on the PayCard (payment #3). Therefore, the total possible compensation for completing the study is \$150. All compensation is loaded onto one PayCard registered specifically to the participant.

In addition, participants enrolled in the hybrid CR program will be permitted to keep the study-provided stationary bike and adjustable ankle/wrist weights upon completion of the study, which has an estimated value of \$350.00 - \$425.00 when purchased as new.

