Loss of Confidentiality: A potential risk from this study is the violation of the participant's privacy, since patient medical information will be used as a source of data. We have measures in place to protect participant privacy and confidentiality.

A NYP-VCR clinical CR supervisor and physical therapist ([name]), exercise physiology scientist ([name]), and internal medicine physician ([name]) will be on-call during video visits to provide study personnel with assistance if participants experience any adverse responses to exercise during their participation in this pilot study.

**Benefits:** There is no direct benefit to subjects who participate in this study.

**Alternatives:** The alternative is not to participate. Additionally, the Principal Investigator may withdraw participants from the study after enrollment upon further examination of eligibility criteria and/or at her

professional discretion. Participants will be informed that they have the option to skip study-based questions and/or not complete all surveys. In turn, the number of skipped questions and/or incomplete surveys will become part of study analysis.

**Data and Safety Monitoring:** Data and safety monitoring will be conducted by the study staff as directed and overseen by the principal investigator. Investigators and research assistants will meet weekly to discuss any issues or concerns with the study, in particular, whether there were any unexpected complaints about the study procedures or questionnaires, or whether there were any breaches in data confidentiality (which will be reported to the IRB as required by policy). If unexpected complaints about the procedures or questionnaires are generated, then the study may be stopped or altered prior to recruiting the full sample.

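### The exit interview and final questionnaires follow Session 24, with no stated route to them for participants who stop or are withdrawn before it

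*Combined protocol and SAP*

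**What the plan says.** All of the following is in the combined protocol and SAP.

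- Section 3, Post-Intervention: "After completing the last CR session (Session 24), participants will be asked to complete post-intervention questionnaires and an exit interview". Both are due within a week of that session. The only exceptions mentioned concern lateness, such as illness or a holiday. In person or by telephone are both allowed.
- Section 3, Exit Interview: "After each participant completes the post-intervention questionnaires, they will participate in a 30-minute exit interview". Its purpose is given as: "The goal is to assess participant-level barriers and facilitators to participating in and implementing the pilot study".
- Section 3, Post-Intervention Questionnaires: "The same battery of questionnaires will be administered half way into the intervention (CR Visit 12"). This is a mid-program assessment by questionnaire, with no interview.
- Compensation: "Following successful completion of CR session 24 and post-intervention assessments, they will be compensated an additional" $50 (payment #3).
- Aim 2 Analysis: barriers and acceptability are to be compared between participants with high and low fidelity to the hybrid program, and "among those in the THCR vs. traditional arms of the study".
- Early exit is foreseen. Under Alternatives, "the Principal Investigator may withdraw participants from the study after enrollment". Under Sample Size and Power Estimates, the investigator will "use estimates from these studies (e.g., standard deviations, attrition rates") to plan the next trial. Feasibility criterion (3) is met when 70% of an arm completes the outcome assessments.

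**The concern.** The study is motivated by low participation in, and adherence to, cardiac rehabilitation. Its interview is meant to find out what gets in the way of participating. People who stop are the most direct source on why people stop, yet the described path to the interview runs through the last session. If that path is followed literally, the barrier themes come from people whose barriers did not prevent them from reaching Session 24.

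Three uses of the data would be affected:

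- The Aim 2 themes are meant to shape implementation strategies for the next trial.
- The fidelity contrast would have its low end thinned. Table 1 counts fidelity out of all 24 sessions, so early stoppers would presumably fall there.
- The contrast between arms would be skewed if stopping is more common, or happens for different reasons, in one arm.

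The final FIM, AIM and IAM percentages have the same limitation. Table 1 gives them no denominator, although it defines one (all randomised to the arm) for program initiation and for assessment completion.

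**Working it through.** The plan gives no figure on this point to reproduce. The check is mainly a reading of which data a participant leaves, according to when he or she stops.

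**Step 1. Data planned by stopping point (section 3)**

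| Participant | Questionnaires | Exit interview |
|---|---|---|
| Reaches Session 24, however many sessions were missed | Mid-program (if Visit 12 was reached) and final | Planned |
| Stops after Visit 12 | Mid-program battery, including FIM/AIM/IAM and determinants questions; weekly surveys; home-session surveys (THCR) | No stated route |
| Stops before Visit 12 | Baseline and weekly surveys; onboarding feedback and home-session surveys (THCR, if those steps were reached); no FIM/AIM/IAM | No stated route |

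Three things follow:

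- The affected group is those who never attend Session 24. It is not everyone with poor attendance.
- The questionnaire gap is partial and the interview gap is complete.
- Before Visit 12, a traditional-arm stopper leaves less than a hybrid-arm stopper, because onboarding and home-session surveys exist only in the hybrid arm.

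**Step 2. Is there another route?** Study Purpose and Rationale mentions focus groups as a possible addition or alternative to interviews, but Study Procedures describes none. The exceptions under Post-Intervention cover lateness only. Alternatives allows withdrawal but attaches no final contact to it.

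**Step 3. Illustrative size.** Inputs are 20 per arm (Overview of Study Design) and the 70% threshold in criterion (3). The assumption, which the documents do not make, is that missing outcome assessments and never reaching Session 24 are the same people.

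- Criterion (3) is just met: 0.70 × 20 = 14 complete, so 20 − 14 = 6 per arm and 2 × 6 = 12 of 40 are without a planned interview.
- If 20% stop: 0.20 × 20 = 4 per arm, 8 of 40.
- If 10% stop: 0.10 × 20 = 2 per arm, 4 of 40.

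**Step 4. Why the denominator matters for FIM (invented counts, illustration only).** Suppose 14 of 20 THCR participants give a final FIM and 12 of them score 4 or more.

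- Responders: 12/14 = 86%.
- All 20 randomised, with the 6 missing counted as not adequate: 12/20 = 60%.
- All 20 randomised, with the 6 missing counted as adequate: (12 + 6)/20 = 90%.

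The exact percentages mean nothing. They show that the responder figure cannot be read without both counts beside it.

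**The case against.** The strongest reply is that silence is not exclusion. The plan describes the intended path. The Randomization text lists an exit interview for the traditional arm without making it conditional on Session 24. Consent pages and supplementary material are not available and may contain a withdrawal procedure. Staff hold contact details and could telephone anyone. This stands in part: a reader might infer that early stoppers are barred from the interview, and the documents do not say so. What remains is that nothing in the available text asks staff to make that call, and every timing rule is counted from Session 24.

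A second reply is that incomplete surveys are already to be counted and analysed (Alternatives), and that timely completion is to be recorded (section 2, Sample Size and Power Estimates). This also stands and narrows the questionnaire part to reporting both denominators. It does not supply an interview.

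A third reply is that the size is assumed. That is correct. Criterion (3) concerns the outcome assessments, such as the walk test and the DUKE. It is a floor for a go decision and not a forecast of dropout, so a reader should not take 6 of 20 as expected loss. Nor would it help to calculate the chance of hearing a barrier held only by stoppers. Supposing that no finisher holds it fixes the answer in advance, and the Visit 12 determinants questions might pick it up anyway.

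Finally, a reader might see a contradiction between the 3-month follow-up and the 6 months allowed to the hybrid program. Overview of Study Design uses the 3-month visit as the name of the program-completion visit, so the two differ only if a program overruns. That is a conditional matter of definition and is not pressed here.

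**Conclusion.** The concern holds in a limited form. On the available text, the exit interview and final questionnaires follow Session 24, and no route is stated for those who stop or are withdrawn sooner. The interview evidence on barriers, and the Aim 2 contrasts by fidelity and by arm, would therefore lean towards people who reached Session 24. The direction follows from the wording. The size does not, because no dropout rate is given. Up to 6 of 20 per arm is the figure if all the missing assessments tolerated by criterion (3) were people who never reached Session 24.

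A reader might infer that the go/no-go decision is compromised. It is not: the two primary endpoints and the five feasibility criteria do not use the interview or the FIM, AIM and IAM. The change is worth making because Aim 2 rests on these interviews and the remedy is cheap. A late call remains possible, but the plan would not prompt one.

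**What to change.** 1. In both arms, offer the exit interview and final questionnaires at Session 24, at discontinuation of the program, or at the end of the 6-month maximum, whichever comes first, using the telephone option already in the plan. The 6-month limit is written only for the hybrid program, so state that it also applies to this contact in the traditional arm.
2. Make the offer to anyone who has not withdrawn consent to contact. Keep those who stop attending, those the investigator withdraws and those who withdraw consent as separate categories.
3. Do not make the interview depend on completing the questionnaires.
4. Report FIM, AIM and IAM with both the number of responders and the number randomised to THCR, and show Visit 12 scores for those who stopped after it.

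Cost: a protocol amendment of a few sentences, and a decision on whether early stoppers receive any of payment #3. Each contact takes 20 minutes of questionnaires plus a 30 to 45 minute interview, so 50 to 65 minutes, followed by transcription and coding. At the illustrative 6 per arm this is 6 × 50 = 300 to 6 × 65 = 390 minutes, or 5 to 6.5 hours of contact per arm. Some will decline, so the gap narrows without closing.

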If during the standard of care visit the treating CR clinician determines that the patient continues to demonstrate they are at low-to-moderate risk and has adequate pulse-oximeter readings, a member from the CR team will message a member of the research team (waiting "on standby") via Epic message, email, or telephone. This message will indicate that the patient *continues* to be eligible for the study and thus may be approached for written/signed consent and possible randomization. If the participant does not meet eligibility criteria, the participant will be informed and thanked for their time and will not continue with study activity.

Phase 2. A member of the research team will then approach the patient after their standard of care CR evaluation visit to review the study in more detail and explain participation. If the verbal consent for screening and screening questions have yet to be conducted, it will take place at this time, followed by the written/signed consent process for participation in the overall study. The consent process will begin with a concise and focused presentation of the key information about the research study and will present information in sufficient detail, including details about randomization. Potential subjects will have adequate time to review the documents in a private setting as well as an opportunity to discuss the information provided. If the patient prefers to set up a separate phone call or Zoom videoconference before or after the CR evaluation visit to discuss the study's informed consent document, we will accommodate accordingly. If the consent discussion for participation in the overall study takes place via Zoom, the research team member who conducts the informed consent process will remotely witness the patient signing the consent. The participant will then be asked to mail back the partially executed consent form in a prepaid envelope. Upon receipt of the partially executed consent document, the research team member will countersign the form and document the details of the consent process. In turn, the participant will be provided with a copy of the fully executed consent document.

**Baseline Questionnaires and Randomization:** Upon obtaining signed consent, research personnel will administer baseline questionnaires and then open an envelope with information about which group the participant has been allocated to via randomization.

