Baseline Questionnaires (10 mins): Participants will be asked to complete a set of questionnaires to collect physical activity and exercise sensitivity measures immediately after the written/signed consent process (this is the preferred option). However, if the participant has scheduling conflicts and/or time constraints at the conclusion of their standard of care CR evaluation visit, the research team will provide hard copies of the questionnaires to the participant and give them the option to complete the questionnaires later but prior to their first clinic-based CR Session (Session 1). Research personnel will follow-up by phone and/or email/text and depending upon participant preference, the baseline questionnaires may be completed verbally with a member of the research team or via a secure Qualtrics link. Completion reminder attempts initiated by the research team will be documented.

Randomization: A member of the research team will open an envelope with information about which group the participant has been allocated to via randomization. Computer generated random allocation in SAS will be used to allocate patients to hybrid CR or traditional CR in 1:1 ratio; this process will take place prior to study initiation. Patients randomized to the traditional CR program will complete 24 clinic-based sessions according to NYPH's existing protocols. Patients randomized to the THCR program will complete 5 clinic-based and 19 home-based sessions according to protocols and intervention components (details provided below). If the patient is allocated to the hybrid CR model, research personnel will confirm the participant's home address and preferred days and times of shipment and assembly service for the home-based exercise equipment, as well as onboarding session part 2 (details provided below). In cases where the participant owns and specifically requests to use a comparable home-based exercise bike (e.g., Peloton Bike), the participant will be given the option to use their own equipment after being found acceptable by the research/CR team. (Note: this is what would be done according to standard of care if the participant was not enrolled in the study.) They will also be asked to stay 15-

Revised 7/10/2025 Page **5** of **15** 

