Home-based CR Sessions (Session 3-7, 9-15, 17-23; 60 mins): Only those allocated to the hybrid CR program (active arm) will complete home-based CR sessions. All home-based CR sessions will be administered by Research Personnel on a secure Philips Healthcare's eCC Video Visit Platform and will align with what the CR clinician/team would do as standard of care. In the case technical issues occur with the eCC Video Visit Platform, Zoom will be used as the virtual platform to support the 2-way video visit. In the case technical issues occur with the pulse oximeter or blood pressure cuff/monitor, standard of care procedures will be used (e.g., use alternative device, manually determine pulse). The first two home-based CR sessions (Session 3 & 4) will be supervised via a 2-way video visit for the full duration of the session (50-60 mins), while subsequent home-based sessions (Session 5-7, 9-15, 17-23) will be partially supervised (20-30 mins) during the aerobic exercise component. During the first week of home-based CR sessions, the participant's physical home address (e.g.. 1234 Main Street Apt. A, Small Town 10001) as well as the name and phone number of an emergency contact will be confirmed should the participant require any emergency assistance during the CR sessions. Prior to beginning of each home-based session, participants will gather the following equipment: pulse oximeter (attached to a

lanyard), blood pressure cuff, blood pressure monitor, Samsung Tablet, adjustable ankle weights, a chair, and water. Details of the home-based CR sessions are outlined below.

Home-based CR Activity	Measurements	Equipment	Duration
Pre-Exercise Surveys	Exercise Location survey Hybrid CR Pre-Exercise Check In survey	Samsung Tablet	2-3 mins
Resting Vitals	Blood Pressure Heart Rate Oxygen Saturation	Samsung Tablet Blood Pressure Monitor Pulse Oximeter Chair	5 mins
Warm-up	-	-	3-5 mins
Aerobic Exercise	Heart Rate Oxygen Saturation RPE	Samsung Tablet Stationary Bike Pulse Oximeter Borg RPE scale	30 mins
Strength Training	Heart Rate Oxygen Saturation	Adjustable Ankle Weights Chair Pulse Oximeter	15-20 mins
Cool-down	-	-	2-3 mins
Post-exercise surveys	Strength Training survey Satisfaction survey	Samsung Tablet	2-3 mins
Recovery Vitals	Blood Pressure Heart Rate Oxygen Saturation	Samsung Tablet Blood Pressure Monitor Pulse Oximeter Chair	2-3 mins

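### The post-intervention FIM, AIM and IAM ratings are listed for in-person or telephone completion only, with no self-completion link and no separation from the staff who deliver the THCR home sessions

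*Combined protocol and SAP*

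**What the plan says.** Section 3, Post-Intervention, gives two routes for the final questionnaires. In the first, "participants will be given the option to complete the questionnaires and exit interview in-person, at the NYP-VCR clinic immediately following the last CR session". The second is a telephone contact on another day; the choice of time and place is put as "immediately following the last CR session or at a separate day and time via telephone". The next paragraph, Post-Intervention Questionnaires, places the FIM, AIM and IAM in this battery and repeats the battery at CR Visit 12, without giving a mode for that visit.

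Nobody is named as collector of the final ratings. The research team appears in the Post-Intervention paragraph only for reminders: "Completion reminder attempts initiated by the research team will be documented".

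Table 1 makes the percentage "of participants who report adequate feasibility of the THCR intervention" a secondary endpoint, defined as a mean of at least 4 over four items scored 1 to 5. The AIM and IAM versions are tertiary and use the same cut-off.

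On delivery, the Home-based CR Sessions paragraph states: "All home-based CR sessions will be administered by Research Personnel".

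Other questionnaires have a private route. For baseline, "the baseline questionnaires may be completed verbally with a member of the research team or via a secure Qualtrics link", and paper copies may be handed out. Onboarding feedback can be given by phone or through a link that is emailed or texted. The weekly surveys are Qualtrics surveys whose links go to both arms.

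**The concern.** The FIM, AIM and IAM ask patients for an opinion of the programme they have just finished. Such answers can drift upwards when they are given to someone connected with the programme. In the THCR arm that person could well be a member of the research team, which ran both onboarding sessions and the home sessions. Of the questionnaires whose mode the protocol describes, the ones carrying these endpoints are the only ones without a listed link.

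The exposure may also differ by arm. CR clinicians deliver the clinic-based sessions, so a traditional-arm patient who answers research staff is not rating the people who treated them. A THCR patient might be.

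What is at stake is how far the reported percentages for THCR can be trusted. They are the plan's quantitative evidence on how patients judge the intervention.

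**Working it through.** The plan states no figure for this risk, so there is none to reproduce. The check sets the passages side by side and then does some arithmetic for scale.

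**1. Mode of completion by instrument (Section 3)**

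| Instrument | Listed modes | Self-completion listed? |
|---|---|---|
| Baseline questionnaires | Given by research personnel, on paper, spoken, or Qualtrics link | Yes |
| Onboarding feedback | Phone, or emailed/texted link | Yes |
| Weekly surveys | Qualtrics | Yes |
| Visit 12 battery | Not stated | Not stated |
| Post-intervention battery (FIM, AIM, IAM) | In person or telephone | No |

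The onboarding text treats phone and link as alternatives. This supports reading the telephone route at the end of the study as spoken answers.

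**2. Who delivers and who collects**

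- Home sessions are 3–7, 9–15 and 17–23, so 5 + 7 + 7 = 19 of 24, all run by research personnel.
- Session 12 falls in the 9–15 block. For THCR patients the mid-study battery is therefore tied to a home session run by research personnel.
- At baseline, "research personnel will administer baseline questionnaires". This is the closest guide to who would handle the final battery, but it is not a statement about it.
- No section assigns the final ratings to a collector outside the delivery team or describes another safeguard.

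**3. Sensitivity of the cut-off**

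- Answers 4, 4, 4, 3: (4 + 4 + 4 + 3)/4 = 3.75, below 4, so not adequate.
- One item raised by one point: (4 + 4 + 4 + 4)/4 = 4.0, so adequate.
- Weight of one patient: 1/20 = 5 percentage points if all 20 THCR patients respond. Two to four such patients move the endpoint 10 to 20 points; that number is an assumption.

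**4. Effect on the lower confidence limit**

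Aim 1 Analysis plans a one-sided 95% lower limit for each proportion. The method is not named; I take the exact limit, the 5% quantile of a Beta(x, 20 − x + 1) distribution.

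| Rated adequate | Observed | Lower limit |
|---|---|---|
| 12/20 | 60% | 39.4% |
| 14/20 | 70% | 49.2% |
| 16/20 | 80% | 59.9% |
| 18/20 | 90% | 71.7% |

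Two patients crossing the cut-off, from 14 to 16, raise the limit by 59.9 − 49.2 = 10.7 points.

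**5. Illustration over a range of assumed bias**

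Let the true adequate rate be 60%, and let a fraction q of the other patients rate up across the cut-off. The expected rate is 0.60 + 0.40 × q. The chance of 14 or more out of 20 follows from the binomial distribution.

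| q (assumed) | Expected rate | Chance of at least 14/20 |
|---|---|---|
| 0% | 60% | 25% |
| 10% | 64% | 38% |
| 25% | 70% | 61% |
| 50% | 80% | 91% |

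The 60% rate, the values of q and the 14/20 mark are yardsticks of mine. The protocol sets no target for these scales and gives no size for the bias.

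**The case against.** A reader might infer that patients can rate THCR only to the people who ran their home sessions. The documents do not support that. No collector is named, and research personnel is a role that may cover several people. In person need not mean spoken either: paper copies are already used at baseline, and Session 24 itself is run by CR clinicians. Lack of privacy is certain only for the telephone route, and the number of patients who will choose it is unknown. This part of the objection stands.

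A reader might also infer that the bias could tip the study into declaring THCR feasible. The Feasibility Criteria paragraph does not support that. Its five criteria are recruitment, initiation, assessment completion, adherence and fidelity, and the three scales are not among them. The scales still have a role: Aim 1 Analysis says the endpoints, alongside the criteria, inform the decision on a full trial. Aim 2 Analysis will compare acceptability between arms, although it works mainly from interviews and does not say whether the AIM score is used.

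The ratings already come before the exit interview, so order is not a defect. The arithmetic shows leverage and is not evidence that bias will occur.

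Finally, the two routes are offered to suit patient preference, and timely survey completion is itself studied. A rule that allowed only a link could cost responses, and with 20 patients missing scales also move the endpoint. That stands as a reason to keep a fallback.

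**Conclusion.** The point holds as a minor weakness of design. For the FIM, AIM and IAM the protocol lists two contact-based routes, omits the self-completion link it uses elsewhere, and does not separate collection from delivery of the home sessions. This leaves subjective threshold endpoints open to socially desirable answers, and the likely direction favours THCR.

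The direction is a judgement from general principle. The size cannot be estimated from the documents; what can be stated is the leverage of 5 points per reclassified patient, given complete THCR response. No stated feasibility criterion would be crossed as a result. The consequence is less trustworthy secondary and tertiary percentages feeding a decision they inform but do not determine.

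**What to change.** In Section 3, Post-Intervention and Post-Intervention Questionnaires, state that:

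- the FIM, AIM and IAM are self-completed by default, through the existing Qualtrics link or on paper placed in a sealed envelope;
- staff-read completion is a fallback for patients who cannot self-complete, or have not done so within the 1-week window;
- the mode used is recorded for each patient;
- the same rule applies to the Visit 12 battery, with staff-read use at that visit limited in the same way.

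The cost is a few sentences of protocol text. The platform is in place, reminders are already logged, and the exit interview, sample size and analysis do not change. Some patients may need a reminder and completion could fall slightly, which the staff-read fallback limits. Recording the mode also lets the report show how many ratings were self-completed.
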